2.3 ADDITIONAL SECONDARY EFFICACY OBJECTIVES

Additional secondary efficacy objectives of the study (Cohort 2) are:

- To demonstrate that ZX008 is superior to placebo on the following endpoints:
 - The number of convulsive seizure-free days.
 - The proportion of subjects who achieve $\geq 25\%$ or $\geq 75\%$ reductions from baseline in convulsive seizure frequency.
 - The change from baseline in non-convulsive seizure frequency.
 - The change from baseline in convulsive + non-convulsive seizure frequency
 - The incidence of rescue medication usage
 - The incidence of hospitalization to treat seizures
 - The incidence of SE

- The change from baseline in health-related quality of life (HRQOL) measured using the Pediatric Quality of Life Inventory™ (PedsQL) Generic Core Scale
- The change from baseline in PedsQL Family Impact module score
- Change from baseline in subjects' quality of life measured using the Quality of Life in Childhood Epilepsy (QOLCE)
- The change from baseline in the HRQOL of the parent/caregiver using the standardized measure of health status (EQ-5D-5L) scale
- The change from baseline on the impacts of the condition on parents and the family using the PedsQL family impact module.
- Clinical Global Impression – Improvement (CGI-I) rating, as assessed by the principal investigator
- CGI-I rating, as assessed by the parent/caregiver

The safety objectives of the study are:

- To evaluate the safety and tolerability of ZX008 administered as a single oral dose when added to standard of care treatment for Dravet syndrome (CLB + VPA; CLB + VPA + STP) (Cohort 1)
- To compare the safety and tolerability of ZX008 to placebo with regard to AEs, laboratory parameters, physical examination, neurological examination, vital signs (blood pressure, heart rate, temperature, and respiratory rate), ECGs, ECHOs, and body weight, and assessment of cognitive function (Cohort 2).

The PK objectives of the study are:

- To assess the PK profile of ZX008 administered as a single oral dose with CLB + VPA or with CLB + VPA + STP in subjects ages 2-18 years of age with Dravet syndrome (Cohort 1).
- Model PK of ZX008 in single and multiple dose regimens using fenfluramine/norfenfluramine concentration-time data from subjects in Cohorts 1 and 2.

2.4 EXPLORATORY OBJECTIVE

Exploratory objectives of this study [Cohort 1 and 2 will be evaluated separately] include:

- The change from baseline in health and social care resource use including planned and unplanned hospital visits, use of ambulances, general practitioner (GP) visits, speech and language therapy utilization, occupational and physical therapy utilization.
- Change from baseline in sleep quality.

- Change from baseline in mealtime behavior.
- Effect of study medication on sleepiness (Karolinska Sleepiness Scale).
- Assessment of a Dravet syndrome composite endpoint including seizure frequency and severity and subjective patient-relevant outcome measures (eg, behavior, sleepiness, etc) using data from the collected rating scales will be performed.

2.5 STUDY ENDPOINTS

2.5.1 Efficacy Endpoints (Cohort 2 only)

The efficacy endpoints of the study are:

- Number of seizures by type
- Convulsive seizure-free interval
- Number of instances of rescue medication use and number of doses
- Number of inpatient hospital admissions due to seizures
- Duration of prolonged seizures (seizure type that, during baseline, had duration > 2 minutes)
- Number of episodes of SE
- QOLCE to measure changes in quality of life of the subject
- HRQOL based on the PedQL Generic Core Scale
- HRQOL of the parent/caregiver using the EQ-5D-5L scale
- Impact of the condition on parents and the family using the PedsQL Family Impact Module.

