10. STATISTICS

10.1 DETERMINATION OF SAMPLE SIZE

No formal hypothesis tests are planned for the PK endpoints studied in Cohort 1. Thus, the sample size for Cohort 1 is based on practical considerations including the expected availability of appropriate subjects. The PK data from Cohort 1 will be used in combination with PBPK models that are being developed using robust data from adults and from existing PBPK models for the concomitant medications. In this way, the data from ZX008-1504 will be leveraged with existing PK information on fenfluramine, stiripentol, clobazam and valproate acid to confirm the expectations derived from the mechanism-based PBPK models. Analysis of the data in this way allows for the confirmation of the appropriateness of the extension of the PBPK model from adults to children and a robust assessment of the potential for a drug-drug interaction between ZX008 and stiripentol while limiting exposure to a smaller number of patients. The 18-20 subjects targeted for the PK phase of the study is expected to be sufficient to allow for the extension of the PK information gained in the ongoing PK study in adults and existing PBPK models to pediatric patients with Dravet syndrome.

The sample size for Cohort 2 is based on results from Study 1, the randomized, placebo-controlled study in subjects with Dravet syndrome sponsored by Zogenix (Lagae 2017). The standard deviation (SD) of the percentage change in seizure frequency from baseline to the end of study (Day 99) was 50% for the 0.8 mg/kg/day group and 69% for the 0.2 mg/kg/day. For the sample size calculation for Cohort 2, the SD is assumed to be intermediate between the SDs observed in the high and low dose groups in Study 1. Assuming an SD of 58, and using a two-sided test at the $\alpha=0.05$ significance level, a sample size of 45 subjects per treatment group affords 90% power to detect a difference in mean change in seizure frequency from baseline of 40 percentage points. Thus, the total sample size for Cohort 2 is planned to be approximately 90 subjects (45 per arm).

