6.3.3.6 Incidence of Rescue Medication Usage

Use of rescue medication is recorded on the daily diary. In the event of prolonged seizures or status epilepticus, rescue medication is administered according to each subject's personalized regimen consisting of one or more medications. If the first rescue administration does not control the seizures, a second or even third round might be administered. The second and third round might use medications or doses different from the first round of rescue meds.

Rescue medication will be summarized by treatment group and by active treatment vs. Placebo for the following:

- The number of days rescue medication was taken (normalized to 28 days) will be summarized for the T + M period by the mean, standard deviation (SD), median and range. The ZX008 treatment group will be compared to the placebo group using a rank ANCOVA analogous to that described in [Section 6.3.1.1](#). Specifically, the ANCOVA will use ranks of rescue medication frequency during T+M as the response, and will incorporate treatment group as a classification factor and the ranks of rescue medication frequency during Baseline as a covariate.

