6.3.3.8 Incidence of Status Epilepticus

The incidence of status epilepticus will be evaluated based on cases captured as such with emergency treatment at treatment centers and entered as adverse events into the safety database, and also as convulsive seizures lasting longer than 10 min from the seizure diary. According to the International League Against Epilepsy definition, seizures over five minutes duration are to be considered SE.

The number and percentage of subjects with status epilepticus recorded as an AE will be presented by treatment group for the baseline and the T+M period per 28 days.

In addition, from the diary data, change from baseline in the number and percentage of convulsive seizures with duration >10 min for the baseline and T+M period will be reported. The number and percentage of subjects will be presented by treatment group for the baseline and the T+M period per 28 days.

All seizures recorded in the AE database as status epilepticus should also be included in the seizure diary. An edit check will be performed to identify the overlap between seizures related to hospitalization for SE and seizures entered into the diary as seizures > 10 min. (The definition of SE includes seizures lasting 5 min or longer, so not all SE will be recorded in the >10 min category.)

To ensure that all instances of SE are accounted for, a composite endpoint will be constructed that combines episodes of SE recorded as AEs with any other convulsive seizure with a duration > 10 min. The ZX008 and placebo groups will be compared on the composite endpoint using a Cochran-Mantel-Haenszel test with age group as stratification factor.

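### The SAP's only between-arm test of status epilepticus does not say how the composite is scored and ignores Baseline; scored yes/no, it can lose power unless episodes are rare

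*Protocol*

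**What the plan says.** Two places in the protocol describe what is to be learned about SE. Section 2.5.1 lists "Number of episodes of SE" among the efficacy endpoints. Section 2.3 lists "The incidence of SE" among the endpoints on which ZX008 is to be shown superior to placebo.

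SAP 6.3.3.8 reports SE recorded as AEs, and diary convulsive seizures over 10 minutes, for Baseline and for Titration plus Maintenance (T+M), both descriptively. It then forms the composite and gives one comparison: "The ZX008 and placebo groups will be compared on the composite endpoint using a Cochran-Mantel-Haenszel test with age group as stratification factor". There is no Baseline term and no statement of how the composite is scored. SAP Appendix 1 plans Table 14.2.9.1b on the number of SE episodes.

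Rescue medication is also worded as an incidence objective in Protocol 2.3. For it, SAP 6.3.3.6 uses a rank ANCOVA with "the ranks of rescue medication frequency during Baseline as a covariate".

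**The concern.** Because the scoring is unstated, two analysts could follow SAP 6.3.3.8 and run different tests. The word incidence suggests yes/no per child over the 15-week T+M period. On that reading, a child who falls from 12 long seizures to 1 scores the same as a child who stays at 12. A frequently affected child can benefit a great deal and still have one event. A mildly affected child may have none in either arm.

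On either reading, Baseline goes unused in the test, so between-child variation and any chance imbalance in prior SE stay in the comparison. The data for adjustment already exist, and the SAP applies the method to a closely related endpoint. At stake is a real effect on SE being missed or shown less clearly than the data allow.

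**Working it through.** **The plan's own figure.** Protocol 10.1 states that "a sample size of 45 subjects per treatment group affords 90% power", with SD 58 and a difference of 40 points, two-sided alpha 0.05. Check: n = 2(z₀.₉₇₅ + z₀.₉₀)² × SD²/Δ² = 2 × (1.960 + 1.282)² × 58²/40² = 2 × 10.51 × 2.1025 = 44.2, so 45. Power at 45 is 90.5% (normal) or 89.9% (t). The figure reproduces, but it concerns the primary endpoint. Neither document gives a power, an episode rate or an effect for SE.

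**Model (assumed).** Each child has a rate λ per 28 days drawn from a gamma distribution with mean m and shape k (small k means wide spread between children). Baseline count ~ Poisson(42/28 × λ) = Poisson(1.5λ). T+M count ~ Poisson(105/28 × λ × θ) = Poisson(3.75λθ), with θ = 1 on placebo. There is no dropout.

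**What a yes/no score sees.** P(any episode) = 1 − (1 + 3.75mθ/k)^(−k). Take k = 1 and a true halving of the rate (θ = 0.5):
- m = 1: placebo 1 − 1/4.75 = 0.79, ZX008 1 − 1/2.875 = 0.65, a gap of 14 points.
- m = 3: placebo 1 − 1/12.25 = 0.92, ZX008 1 − 1/6.625 = 0.85, a gap of 7 points.

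The more frequent the episodes, the less of the same halving is visible.

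**A low anchor from the documents.** In the parent survey in Protocol 1.1.1, about one-third of patients had an SE emergency admission in 12 months and 10% had four or more. A negative binomial fitted to those two figures has mean about 1.1 per year and shape about 0.23. Check: P(0) = (1 + 1.1/0.23)^(−0.23) = 0.67. Per 28 days the mean is 1.1 × 28/365 = 0.08. This covers emergency admissions only; the composite adds diary seizures over 10 minutes.

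**Simulated power, 45 per arm, 60% reduction (θ = 0.4), child's rate constant across periods:**

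| Mean per 28 days | Shape | Yes/no CMH | Rank ANCOVA with Baseline | Gap (points) |
|---|---|---|---|---|
| 0.08 | 0.23 | 20–21% | 24% | 3–4 |
| 0.2 | 0.3 | 27% | 38% | 11 |
| 0.2 | 0.7 | 45% | 55% | 10 |
| 0.5 | 0.3 | 25% | 52% | 27 |
| 0.5 | 0.7 | 45% | 79% | 34 |
| 1 | 0.3 | 21% | 68% | 47 |
| 1 | 0.7 | 41% | 92% | 51 |

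With no true effect, both tests reject in about 4–5% of trials.

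**Rates that vary between periods.** Adding independent period-to-period variation (gamma, variance 1) shrinks the gap. At m = 0.2, power becomes 23% v 27% and 32% v 36%. At m = 1, k = 0.7, it becomes 31% v 57%. Across runs with and without such variation, the gap is about 0–2 points at 0.05–0.08, 2–9 at 0.2 and 8–33 at 0.5. The largest table entries sit 1 to 2 points above these ranges, within simulation error (about ±2.5 points on a power figure).

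**If the CMH is run on counts.** At m = 1, k = 0.7, a CMH score test on counts has 74% power, between 41% (yes/no) and 92% (rank ANCOVA). With a 50% reduction, k = 1 and m = 0.5, the three figures are 34%, 57% and 65%. At the SAP's 40 per arm the pattern is the same.

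**The case against.** A reader might infer that the planned SE analysis loses most of its power. The documents do not support that, because they give no composite rate, spread or effect. At the rate of emergency-admission SE the tests are nearly equal and all are weak. The composite should occur more often than admissions alone, since it adds long diary seizures in children selected for at least 4 convulsive seizures per 4 weeks, but by how much is unknown.

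A reader might also take the test to be binary. The SAP does not say so, and a CMH score test on counts fits its text. That reduces the loss but does not bring Baseline in.

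Nor is the CMH invalid or off the objective. Randomisation protects its type I error, and a proportion test does answer an objective worded as incidence. Counts and changes from Baseline will be visible descriptively.

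The strongest practical objection is that an episode count is harder to define. Protocol 7.1.1 and 8.1.2 let a series of seizures form one SE, and 8.1.2 has two or more episodes within 24 hours recorded as an SAE of SE. SAP 6.3.3.8 itself needs an edit check for overlap between SE hospitalisations and the diary. Yes/no scoring is robust to this. The objection stands as a condition on the fix.

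Finally, SE lies outside the alpha-controlled hierarchy in SAP 6.1.2 and the trial was not sized for it, which limits the consequences.

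**Conclusion.** The point holds in a limited form. It is documented that the protocol names an episode count, that the sole between-arm test has unstated scoring, and that this test omits Baseline data that the SAP uses for rescue medication. The size of any power loss is conditional: it applies to yes/no scoring and depends on assumed rates, a 60% reduction and gamma-Poisson counts. It runs from negligible when episodes are rare to large at 0.5 or more per 28 days. It is smaller if a child's rate varies between periods or if counts are tested. In the settings simulated, the Baseline-adjusted rank test was no worse than the yes/no CMH beyond simulation error. That makes the change worth its modest cost, though the trial's main conclusions do not depend on it.

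**What to change.** Amend SAP 6.3.3.8 before unblinding:

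- Make the between-arm test a rank ANCOVA of composite episodes per 28 days in T+M. Use treatment and age group as factors and the rank of the same composite rate in Baseline as covariate. SAP 6.3.3.6 names only treatment and ranked Baseline; age group is added here because it is the randomisation stratum and the planned CMH already stratifies on it.
- State one counting rule and apply it identically in both periods. An SE found in both the AE log and the diary counts once, as does a cluster of seizures forming one SE. Say how AE episodes on days without diary data enter the rate.
- Keep the number and percentage of children with any episode, with the age-stratified CMH as a supportive analysis, to address incidence.

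No new data are needed. The cost is SAP text, one model and some work on the counting rule. The rank test gives no direct effect size, so median rates should stand beside its p-value. SE stays outside the alpha-controlled hierarchy.

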2.5.2 Safety Endpoints

The safety endpoints of the study are:

- AEs
- Laboratory safety (hematology, chemistry, urinalysis)
- Vital signs (blood pressure, heart rate, temperature, and respiratory rate)
- Physical examination
- Neurological examination
- 12-lead ECGs
- Doppler ECHOs
- Body weight
- Cognitive Function will be assessed using the cognition domain score on the QOLCE and age-appropriate versions of the BRIEF

2.5.3 Pharmacokinetic Endpoints

The PK endpoints of the study are:

- PK data for all analytes (fenfluramine, norfenfluramine, CLB, n-desmethylclobazam (N-CLB), VPA, and STP) for Cohort 1 will be used for PK modeling
- PK sampling for ZX008 will be performed on subjects in Cohort 2. Fenfluramine/nor-fenfluramine concentration-time data from subject enrolled in Cohorts 1 and 2 will be used to model PK of ZX008 in single and multiple dose regimens

2.5.4 Exploratory Endpoints

The exploratory endpoints of the study are:

- Health and social care resource use including GP visits, speech and language, occupational and physical therapy, in addition to acute hospital and institutional length of stay, loss of work, etc.
- Change in sleep quality assessed by the patient/caregiver
- Change in mealtime behavior assessed by the patient/caregiver
- Sleepiness assessed by the patient/caregiver using the Karolinska Sleepiness Scale
- Composites endpoints that combine objective and subjective measures

3. INVESTIGATIONAL PLAN

3.1 OVERALL STUDY DESIGN AND PLAN

This is a multicenter, two-cohort trial to assess the PK and safety profile of a single dose of ZX008 (fenfluramine hydrochloride) oral solution when added to Dravet syndrome treatment regimen containing VPA and CLB, with or without STP (Cohort 1), followed by a randomized, double-blind, placebo-controlled parallel group evaluation of the efficacy, safety, and tolerability of ZX008 as adjunctive therapy for seizures in children and young adults with Dravet syndrome (Cohort 2). PK and safety data from Cohort 1 from 13 subjects have been collected and evaluated together with data from Study ZX008-1505 (healthy volunteer drug-drug interaction study) and has informed the dose of ZX008 0.5 mg/kg/day, maximum 20 mg/day, to be used in Cohort 2. The current Amendment of this protocol defines the dose for Cohort 2. Approximately 2-3 sites in France and the Netherlands will be involved in the PK portion of the trial (Cohort 1). Up to approximately 30 study sites in Canada, France, Germany, Netherlands, United Kingdom, Spain, and the United States will enroll participants for Cohort 2.

Cohort 1: Subjects will attend the clinical research unit (CRU) for a screening visit up to 14 days before dosing. Eligible subjects will return to CRU on Study Day –1 for an outpatient visit. Inclusion and exclusion criteria will be confirmed, and physical exam, medical history, body weight/body mass index (BMI), vital signs, urine pregnancy test, urine tetrahydrocannabinol (THC), and whole blood cannabinol (CBD) will be obtained. The subject will be discharged from the unit or allowed to stay overnight, as required. After dinner and a light snack prior to bedtime, subjects will be fasted until the next morning. On the following day (Study Day 1), a parent/caregiver will bring the fasted subject to the CRU between 6 AM and 7 AM.

Following blood collection for clinical labs, and vital sign measurements and weight, subjects will be given a light, low fat breakfast, followed by administration of their usual epilepsy medications. Based on the assigned treatment allocation, each subject will then receive the appropriate dose of study medication (ZX008). Subjects receiving CLB and VA at screening will be stratified by age group (< 6 years of age; ≥ 6 of age) and randomly allocated to Dosing Regimen 1 (ZX008 0.2 mg/kg + CLB + VPA) or Regimen 2 (ZX008 0.4mg/kg + CLB + VPA). At least two subjects from each pre-specified age group are to be assigned to Regimen 1; and at least 2 subjects from each group are to be assigned to Regimen 2. Subjects receiving CLB and VA and STP at screening, will be assigned to Regimen 3 (ZX008 0.2 mg/kg + CLB + VPA + STP). Approximately 5 subjects from each age group (< 6 years; ≥ 6 years) should be enrolled in dosing Regimen 3. Details for each regimen are shown in [Table 3](#).

Table 3. Cohort 1 Dosing Regimens

Dosing Regimen	Dosing on Day 1	Dose of ZX008	Age Stratification
#1	CLB + VPA + ZX008	0.2 mg/kg	[n=5]; at least 2 subjects per age group (< 6 and ≥ 6 years)
#2	CLB + VPA + ZX008	0.4 mg/kg	[n=5]; at least 2 subjects per age group (< 6 and ≥ 6 years)
#3	CLB + VPA + STP + ZX008	0.2 mg/kg	[n=10]; total of 5 subjects per age group (< 6 and ≥ 6 years)

Blood samples for PK assessment will be obtained from all subjects through 12-hours post-dose. After the last Study Day 1 blood draw (12 hours post-dose), subjects will be discharged. Twenty-four to thirty-six hours following dosing the subjects will return to the research unit for assessment of vital signs, a final PK sample and to record any adverse events that may have occurred since leaving the CRU. A seizure diary will be provided to record seizure activity between Study Day 2 and the follow-up safety visit (Study Day 15). On Study Day 15, subjects and/or caregivers will return to the CRU for follow-up, including review of diary data. At the conclusion of this portion of the study, eligible subjects from Cohort 1 will be offered enrollment in a separate open-label extension trial and if they choose to do so, they will begin transitioning to study medication (ZX008, 0.2 mg/kg/day), safety and diary data will continue to be captured and the exploratory composite endpoint components will be administered prior to commencement of transitional treatment. The duration of the transition period will not exceed 24 weeks. Subjects may enroll in the separate open-label extension trial when the dose for Cohort 2 has been selected. A schedule of assessments is provided in [Table 1](#).

For Cohort 1 subjects, a follow-up ECHO, ECG, and symptom-directed physical examination will be performed 3-6 months after study drug discontinuation with early termination.

Cohort 2: A 6-week Baseline Period will consist of the establishment of initial eligibility during a screening visit followed by an observation period where subjects will be assessed for baseline seizure activity based on recordings of daily seizure activity entered into a diary. Upon completion of the Baseline Period, subjects who qualify for the study will be randomized (1:1) in a double-blind manner to receive ZX008 (at a dose of 0.5 mg/kg/day, maximum 20 mg/day) or placebo. Randomization will be stratified by age group (< 6 years, ≥ 6 years) to ensure balance across treatment arms, and at least 40% of subjects will be in each age group. All subjects will be titrated to their randomized dose during the Titration Period. Titration will occur in 3 steps starting with a 0.2 mg/kg/day dose of ZX008 (or placebo equivalent) on Study Days 1-7, increased to a dose of 0.4 mg/kg/day on Study Day 8-14, and then increased to a dose of 0.5 mg/kg/day on Study Days 15-21; the maximum daily dose at any point is 20 mg/day. The duration of the titration period will be 21 days.

Following titration subjects will continue treatment at their randomly assigned dose of ZX008 0.5 mg/kg/day (maximum 20 mg/day) or placebo over a 12-week Maintenance Period. Total treatment time from the beginning of the Titration Period through the end of the Maintenance Period is a maximum of 15 weeks. Parents/caregivers will use a diary daily to record the number/type of seizures, dosing, and use of rescue medication. A schedule of assessments is provided in [Table 2](#).

At the end of the Maintenance Period (or early discontinuation), subjects who will not be entering the open-label extension will undergo a taper of 14 days, after which they will be off study medication. Subjects who will be enrolled in the separate open-label extension trial will enter a 14-day transition period.

For Cohort 2 subjects, a follow-up ECHO, ECG, and possibly physical examination will be performed 3-6 months after study drug discontinuation with early termination, or for those subjects who complete the study but do not enter the open-label extension trial.

